## Significant Safety Issue:

A significant safety issue is an issue that could adversely affect the safety of participants or materially impact on the continued ethical acceptability or conduct of the trial.

Comment: A significant safety issue is a new safety issue or validated signal considered by the Sponsor in relation to the study vaccines that requires urgent attention of stakeholders. This may be because of the seriousness and potential impact on the benefit-risk balance of the study vaccines, which could prompt regulatory action and/or changes to the overall conduct of the clinical trial, including the monitoring of safety and/or the administration of the study vaccines.

#### Urgent Safety Measure (USM):

A measure required to be taken in order to eliminate an immediate hazard to a participant's health or safety. Note: This is a type of significant safety issue that can be instigated by either the investigator or Sponsor and can be implemented before seeking approval from HRECs or institutions.

## 8.2 Capturing and eliciting adverse event information

For the period of randomisation to 3 months post randomisation only, the following are non-serious adverse events of interest for this study:

- At injection site:
  - o Reaction (pain, tenderness, redness, swelling) of grade 3 (severe) or 4 (potentially life threatening)
  - o Abscess
  - o Large ulcer (>1.5 cm diameter)
  - o Keloid scar
  - Unusual local reaction
- Lymphadenopathy (in region of injection site)
- BCG osteitis/osteomyelitis
- Disseminated BCG infection (BCG-osis)
- Allergic reaction due to IP
- Fainting episode, seizures and convulsions following IP administration (recorded on the day of IP administration only)

Only these non-serious AE and all SAE, occurring between randomisation and 3 months post randomisation, will be recorded for this study. If applicable, for the remainder of the follow-up period, sites may additionally document participants' AE as required to meet reporting requirements of the applicable HREC/s and/or regulatory authority.

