## Risks related to Placebo injection

Having an injection can sometimes cause very minor pain from the needle or be uncomfortable. The 0.9% NaCl is an inert salt solution that will not cause any degree of local reaction. The placebo injection will be administered by a trained immunization nurse.

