## 6.1 Concealment mechanism

The control group will receive a placebo of 0.9% NaCl. Most people vaccinated with the BCG vaccine develop a papule/blister at the injection site around two-weeks after vaccination. Due to this, even using a placebo, it is not completely possible to blind participants to their treatment group allocation. The outcomes (symptomatic and severe COVID-19 or admission to hospital for COVID-19) are objective measures, it is however still plausible that participant's suspicion of their group allocation might bias the study results. This risk will be mitigated by using a placebo where an element of doubt over treatment allocation may persist even in the absence of scar formation. Members of the study team, except immunisers, will be blinded to the group allocation (by the removal of this variable and all other variables related to BCG from the dataset) until the formal detailed statistical analysis plan is confirmed and signed by all investigators and all data cleaning/preparation is complete.

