## 8.2.2 Non-Serious AE Capture

Non-serious AE of interest are captured:

- On the day of IP administration, recorded by the site personnel
- Within the Vaccine diary (which triggers an alert to the site personnel to contact the participant)
- Through the 3-month questionnaire (questions on injection site evolution)
- Through spontaneous contact (e.g. phone call, electronic message or email) from the participant to the site team.

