#### 8.3 Documentation of AEs

For the purposes of this study the investigator or delegate is responsible for recording the applicable Adverse Events, regardless of their relationship to study vaccines.

The documentation of each applicable AE on the REDCap CRF will include:

- A description of the AE
- The onset date, duration, date of resolution
- Severity
- Seriousness (SAE or not)
- Any action taken (e.g. treatment, follow-up tests)
- The outcome (recovery, death, continuing)
- The likelihood of the relationship of the AE to the trial treatment

All AEs will be followed to resolution or stabilisation, where possible.

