#### 8.4 Assessing the relatedness (causality) of a participant's AE

All non-serious AE of interest and SAE must have their relationship to the trial intervention assessed by the SPI (or delegate) who evaluates the AE based on temporal relationship and their clinical judgment. The degree of certainty about causality will be graded using the categories below.

The relationship of the event to the trial intervention will be assessed as follows:

Code	Causal Relationship	Description
1	Unrelated	The AE is clearly NOT related to the intervention
2	Unlikely	The AE is doubtfully related to the intervention
3	Possible	The AE may be related to the intervention
4	Probable	The AE is likely related to the intervention
5	Definite	The AE is clearly related to the intervention

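### Non-serious allergic reactions are recorded only if attributed to the injection, so a causality judgement comes before the relatedness grading and, on injection day, could be made by unblinded staff

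*Protocol*

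**What the plan says.** Protocol section 8.2 lists the non-serious adverse events of interest. Most are defined by what is seen (for example abscess, large ulcer, keloid scar, regional lymphadenopathy) or by a diagnosis that names the organism. Fainting and seizures are defined by timing, on the day of administration. Allergy is entered as "Allergic reaction due to IP". The section then closes the list: "Only these non-serious AE and all SAE, occurring between randomisation and 3 months post randomisation, will be recorded for this study".

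Section 8.3 makes the investigator or delegate "responsible for recording the applicable Adverse Events, regardless of their relationship to study vaccines". Section 8.4 adds the causality step: "All non-serious AE of interest and SAE must have their relationship to the trial intervention assessed by the SPI (or delegate"), on a five-level scale from unrelated to definite. The outcome table in section 3.2 treats relationship as one of the attributes by which adverse events are reported.

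Section 8.2.2 gives four capture routes. The first is "On the day of IP administration, recorded by the site personnel"; the others are the Vaccine Diary, the 3-month questionnaire and spontaneous contact. On blinding, section 6.1 states: "Members of the study team, except immunisers, will be blinded to the group allocation".

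**The concern.** Causality normally belongs after capture: record the event in both arms, then grade how likely it is that the product caused it. Here, for one item, attribution is the condition for entry. An allergic reaction judged unrelated at that point is never written down, and no later analysis can recover it.

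Two things are at stake. First, the background of allergic reactions from other causes is filtered out, although that background is what lets a reader interpret the count after BCG. Second, if the person applying the filter knows the product, the same rash might be entered after BCG and left out after saline. Immediate reactions are the ones most exposed to this, because they occur while the immuniser is present or close by.

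**Working it through.** The protocol states no figure for this item, so there is none to reproduce. The check is a comparison of passages, followed by a calculation for scale.

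**1. Entry condition against grading.** The closed list in 8.2 requires attribution before entry. Section 8.4 requires every event of interest to be graded from unrelated to definite, and 3.2 reports that grade. If the qualifier is taken at its word, the two lowest grades (unrelated, unlikely) cannot arise for this item. Section 8.3 says relationship should not decide recording. Read together, the three sections do not give one rule for a mild rash that the site thinks has another cause.

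**2. Was another definition available?** Yes. The fainting and seizure item in the same list is defined by timing after injection, with no causal judgement. Allergic reaction is the only clinically non-specific item on the list whose entry rests on an explicit attribution.

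**3. Who judges, and what do they know?**
- Injection day: site personnel record events (8.2.2). Under 5.2.6, issues with immunisation go into the vaccinators' database, and events of interest during administration or the 20 minutes afterwards are documented. Immunisers know the product (6.1). Nothing bars them from making or informing the judgement.
- Later: sections 4.1 and 6.1 describe follow-up staff as blinded, and 8.4 gives relatedness to the site principal investigator or delegate. Both sections concede that the BCG lesion, at about two weeks, can reveal allocation to participants, and participants' spontaneous contact is a capture route.

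**4. Form of the possible distortion.** Let r be the rate of non-serious allergic reactions of any cause in an arm, s the probability that such a reaction is attributed to the injection and so entered, and n the arm size. Then

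recorded count = n × r × s.

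With equal arms and equal true rates, the ratio of recorded counts is s(BCG) / s(saline). If the assessor is blind and the reactions look alike, s is the same in both arms and the ratio is 1; only the background is lost. If the assessor knows the product, the two values can differ. The documents give neither r nor s, so the ratio cannot be computed.

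**5. Scale.** Section 2.3.1 lists allergic reaction or anaphylaxis after BCG among side effects seen in up to 1 in 1000. Section 11.1 gives 3622 per group in the placebo-controlled stage.

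Expected reactions after BCG at that ceiling: 3622 × 0.001 = 3.6.

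Two-sided Fisher exact p-values with 3622 per group:

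| BCG v saline | p |
|---|---|
| 3 v 0 | 0.25 |
| 4 v 0 | 0.12 |
| 5 v 0 | 0.062 |
| 6 v 0 | 0.031 |

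These p-values show only how sensitive such small counts are. The protocol does not specify this test.

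**The case against.** The strongest reply is that this is loose wording with little consequence.

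- **Section 8.3 speaks of applicable events.** That word can be read as deferring to the closed list in 8.2, which would soften the conflict with 8.3. The tension with 8.4 and 3.2 would remain.
- **The qualifier may mean suspected.** Site staff could enter a suspected reaction and the site principal investigator could later grade it unlikely. That is a workable practice, but the text does not say it, and sites may apply the wording differently.
- **Serious reactions are safe.** All SAEs to 3 months are collected without a causality condition (8.1, 8.2.1), and important medical events count as serious. This stands, and limits the point to non-serious reactions.
- **Only immunisers are unblinded.** A reader might infer that staff who know the allocation generally decide what is recorded. Sections 4.1, 6.1 and 8.4 do not support that. Three of the four capture routes go beyond what site staff note on injection day, and under 5.2.6 both arms wear the same sticker during observation. What stands is the injection-day route.
- **Saline is itself an investigational product** (5.2.1.2). A reader might infer that saline recipients will show almost no allergic reactions, citing "The 0.9% NaCl is an inert salt solution that will not cause any degree of local reaction". That sentence concerns local reactions and is not an attribution rule; a blinded assessor could attribute a reaction to saline.
- **No between-arm test of allergic reactions is specified.** Objective 9 is to evaluate safety. This stands, although counts tabulated for two randomised arms will still be read side by side.

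**Conclusion.** The point holds in a limited form. Capture of non-serious allergic reactions is conditional on attribution. This pre-empts the grading in 8.4 and sits badly with 8.3. On injection day, unblinded immunisers may make or inform the attribution, so capture could differ by arm.

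The size is unknown. It is tempting to assume a background rate, suppose that every such reaction is entered after BCG and none after saline, and present the resulting table as a false safety signal. The documents support neither the rate nor the all-or-none recording, and at the protocol's own ceiling of about 3.6 events a 4 v 0 split gives p = 0.12. What can be said is that the counts will be small enough for one or two attributions to alter the impression.

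The conclusion assumes that the qualifier is applied as written and that immunisers have some part in injection-day recording; the protocol permits the latter but does not state it. This is a minor point and does not touch the efficacy objectives.

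**What to change.** In section 8.2, delete the causal qualifier and define the item as an allergic reaction with onset in a stated time window after injection. The window should be the same in both arms and consistent with the 3-month adverse event period in 3.2 and 8.2. Leave attribution to 8.4, made where possible by staff who did not give the injection and do not know the allocation. Align the case report form help text.

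The timing matters. Section 1.3 expected recruitment to end in March 2021, so on that plan the last 3-month window closed about June 2021, before this version (12.0, May 2022). If recording is already complete, new wording cannot recover events that were not entered. The safety report should then state that non-serious allergic reactions were captured conditional on attribution to the injection, and interpret the counts by arm accordingly.

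The cost is one changed list item and its form text, plus a few more unrelated reactions to record and grade. If recording has ended, it is a sentence or two in the report.

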## 8.2.1 SAE capture

SAE are captured on the day of IP administration, as recorded by the site personnel. Information on any SAE since randomisation will be solicited from participants at the 3-month questionnaire. SAE may also be captured via participant notification, in the period

between randomisation and the 3-month questionnaire, such as through spontaneous contact by the participant via call or email, data entered in the Vaccine Diary or the study smartphone app (or equivalent, e.g. weekly phone calls). In cases where a participant does not respond to multiple attempts at contact, over several weeks, the participant's secondary contact will be contacted to confirm their status and record fatal SAE if applicable.

For this study, all SAE will be collected for the period from randomisation to 3 months post randomisation.

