#### Data Retrieval

Data retrieval is further described in Section 9 of this Protocol.

The present study expects that it will acquire some research data from existing administrative and service data sources. In Victoria, for example, this would include obtaining details from the Victorian Department of Health and Human Services (VDHHS) who collects information about presentations to hospitals and emergency departments for medical care in Victoria. Similar processes will be followed in other Australian states. In mainland Europe and Brazil, participants will be required to consent to provide access to their medical records by study staff. In the UK self—reports from participants may be supplemented by tracking of participants using their NHS number or other relevant unique identifiers (provided by

participant), drawing on Hospital Episode Statistics and Office of National Statistics data to track health service use (admissions) and deaths.

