## 7.5.3 Losses to follow-up

Due to the study taking place with healthcare workers during a pandemic, we expect that there may be periods that participants will ignore the smartphone app prompts, phone calls or electronic messages. This includes the eventuality that a participant has been admitted to hospital. The weekly smartphone app prompts will only ask whether the participant has had a fever or respiratory symptom since the last time they answered in the app (date provided). Alternatively, where appropriate, phone follow-up will be used (i.e., Brazil). We deem this very unlikely to annoy participants excessively as they can ignore the notification or call if they are too busy (or withdraw). This will give the project the best chance of having a complete dataset to analyse as they can answer 'Yes' when they get the opportunity and fill in the associated questionnaire. Therefore, we will continue to send out weekly notifications or calls for the entire study regardless of whether participants respond.

In Australia and Europe, if a participant does not answer 2 regular smartphone app prompts (2 consecutive weeks), further attempts will be made to contact them by electronic messages (maximal 3 attempts), phone call (maximal 3 attempts) and email (maximal 3 attempts). If there is still no response, and the participant is not found to have died on medical records, we will try to contact them later (when the workload is expected to have decreased).

In Brazil, if a participant does not answer 3 follow-ups phone contacts (phone call or electronic messages), a home visit may be carried out by study staff. If there is still no response, and the participant is not found to have died on medical records, we will try to contact them later (when the workload is expected to have decreased).

Where secondary contact provided, the study team will follow-up if unable to contact participants.

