#### Serious Adverse Event (SAE) :

Any serious adverse event (SAE) is an untoward medical occurrence that:

- Results in death; or
- Is life-threatening; or
- Requires hospitalisation or prolongation of existing hospitalisation;
  - o Hospitalisation is to be considered an SAE only in the event of an overnight admission. Any elective hospitalisation does not constitute an SAE
- Results in persistent or significant disability/incapacity; or
- Is a congenital anomaly/birth defect

Note: Life-threatening refers to an event in which the participant was at risk of death at the time of the event. It does not refer to an event that hypothetically might have caused death if it were more severe.

Medical and scientific judgement should be exercised in deciding whether an adverse event should be classified as serious in other situations. **Important medical events** that are not immediately life-threatening or do not result in death or hospitalisation but may jeopardise the participant or may require intervention to prevent one of the other outcomes listed in this definition should also be considered serious.

For this study, all SAE will be collected for the period from randomisation to 3 months post randomisation.

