## 11.2 Population to be analysed

The primary analysis of all outcome data will be an intention-to-treat (ITT) analysis including all randomised participants, regardless of whether they received trial drug.

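### The SAE fallback for participants who stop responding looks only for deaths, so non-fatal SAEs in this group are not actively sought although the protocol promises to collect all SAEs to 3 months

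*Protocol*

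**What the plan says.** Protocol section 8.2.1 sets the aim: "all SAE will be collected for the period from randomisation to 3 months post randomisation". It then lists the sources. Site staff record events on the day of injection. After that, "Information on any SAE since randomisation will be solicited from participants at the 3-month questionnaire". In between, the participant may report by call, email, Vaccine Diary, app or weekly phone call. If repeated attempts over several weeks fail, the participant's "secondary contact will be contacted to confirm their status and record fatal SAE if applicable".

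Section 7.5.3 describes periods when participants may ignore prompts and adds: "This includes the eventuality that a participant has been admitted to hospital". The record check it mentions for a participant who stays silent is whether that person has died.

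Section 8.1 makes hospitalisation a seriousness criterion, with a limit: "Hospitalisation is to be considered an SAE only in the event of an overnight admission". Elective admissions are excluded.

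Section 7.3 (Data Retrieval) plans access to hospital data, for example "information about presentations to hospitals and emergency departments for medical care in Victoria", with similar processes in other Australian states. Participants in mainland Europe and Brazil consent to medical-record access, and NHS and national statistics data may be used in the UK. Section 8.2.1 does not name any of these as an SAE source.

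**The concern.** Every route in section 8.2.1 after the injection day depends on the participant answering, except the secondary contact, and for that call the instruction names only fatal events. A long silence is one sign that something serious may have happened, and the protocol says so itself. The written procedure therefore asks least about the group in which an unreported admission is a recognised possibility.

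Safety of BCG in healthcare workers is objective 9. It includes revaccination, and there is no tuberculin skin test screening before vaccination. Section 10.1.2 also has the DSMB review safety at 3 and 9 months, including deaths and ICU admissions. An analysis plan can choose a denominator, but it cannot restore events that nobody asked about, so the capture rule belongs in the protocol.

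**Working it through.** **Step 1. Set the rules side by side.**

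| Protocol section | What it requires or provides | Covers non-fatal SAEs in a silent participant? |
|---|---|---|
| 8.2 and 8.2.1 | All SAEs to 3 months are recorded | Yes, as an aim |
| 8.2.1, 3-month questionnaire and self-report | The participant reports | Only if the participant answers |
| 8.2.1, secondary contact | Confirm status, record a fatal SAE | Not named |
| 7.5.3, record check | Whether the participant has died | No |
| 8.6 | Site reports all SAEs within 24 hours of becoming aware | Only once the site is aware |
| 7.3, periodic questionnaires | Ask about any hospitalisation | Only if answered; not listed as SAE capture |
| 7.3 and 9.2.8, data retrieval | Hospital data and medical records | Possibly; not listed as SAE capture, timing open |

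The aim and the reporting duty cover all SAEs. The two checks written specifically for silent participants name only death.

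**Step 2. Look for a figure in the plan.** The protocol states neither an expected SAE rate nor a 3-month non-response rate. The nearest figure is the 16% loss to follow-up in section 11.1. It agrees with the stated sample sizes: 1 − 6076/7244 = 0.161. But it is the allowance for severe COVID-19 at 6 months, so applying it to the 3-month SAE window is an assumption.

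**Step 3. Illustrate the possible size.** All three inputs are assumed:
- L: share of participants who are persistent non-responders, with no completed 3-month questionnaire
- k: non-fatal SAE rate in them relative to responders
- c: share of their non-fatal SAEs found anyway, including events reported before contact stopped

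Share of non-fatal SAEs captured = [(1 − L) + L·k·c] / [(1 − L) + L·k]

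Example with L = 0.16 and k = 2:
- c = 0: 0.84 / 1.16 = 0.724
- c = 0.5: (0.84 + 0.16) / 1.16 = 0.862
- c = 0.9: (0.84 + 0.288) / 1.16 = 0.972

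| L | k | c = 0 | c = 0.5 | c = 0.9 |
|---|---|---|---|---|
| 5% | 1 | 0.950 | 0.975 | 0.995 |
| 5% | 2 | 0.905 | 0.952 | 0.990 |
| 5% | 3 | 0.864 | 0.932 | 0.986 |
| 10% | 1 | 0.900 | 0.950 | 0.990 |
| 10% | 2 | 0.818 | 0.909 | 0.982 |
| 10% | 3 | 0.750 | 0.875 | 0.975 |
| 16% | 1 | 0.840 | 0.920 | 0.984 |
| 16% | 2 | 0.724 | 0.862 | 0.972 |
| 16% | 3 | 0.636 | 0.818 | 0.964 |

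The share missed runs from 5% to 36% with no recovery, and from 0.5% to 4% with 90% recovery. The answer turns mainly on c, which is the quantity the wording of section 8.2.1 leaves open.

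**Step 4. Effect on the comparison.** With a captured share s in each arm, the observed risk ratio is the true ratio times s(BCG)/s(placebo). Equal shares leave the ratio unchanged and shrink the risk difference. Unequal shares bias both.

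**The case against.** The best defence is that the sentence names fatal SAEs without excluding others. Sections 8.2 and 8.2.1 require all SAEs to 3 months, section 8.3 makes the investigator responsible for recording them, and section 8.6 requires reporting within 24 hours of awareness. A site that is told of an overnight, non-elective admission must record and report it. This stands. A reader might infer that such a reply would produce no SAE record, and the protocol does not support that.

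A reader might also infer that non-fatal SAEs in these participants can never be seen. That is too strong as well. Section 7.5.3 states that "we will continue to send out weekly notifications or calls for the entire study regardless of whether participants respond", plans later re-contact, allows home visits in Brazil, and mentions follow-up through the secondary contact without limiting it to deaths. The schedule in section 7.2 gives the periodic surveys a 42-day window, later questionnaires ask about any hospitalisation, and records may be retrieved. These routes can recover events. They do not fully close the gap: several work only if the participant is reached, the SAE question is confined to the 3-month questionnaire, and section 9.2.8 leaves the timing of data access undetermined.

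A third tempting reading is that unobserved people are counted as event-free and the SAE rate is therefore too low. Section 11.2 says "The primary analysis of all outcome data will be an intention-to-treat (ITT) analysis including all randomised participants", but this is a general statement. The protocol gives no SAE denominator, and the SAP, which is not available here, may define one. Lastly, imperfect blinding makes different non-response by arm conceivable, but nothing in the protocol shows it or its direction.

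**Conclusion.** The point holds as a weakness in a written capture rule. For persistent non-responders, the SAE fallback and the accompanying record check look for death only, while the same protocol recognises hospital admission as a cause of silence and promises to collect all SAEs. Non-fatal SAEs in this group are not actively sought by the stated SAE route.

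The consequence is a risk of under-capture whose size the protocol does not determine. It depends on 3-month non-response, on the SAE rate in those who do not respond, and on recovery through re-contact, later questionnaires and records. The tabulated range of 0.5% to 36% missed reflects assumed inputs and is not an estimate. It does not show that the reported SAE rate will be too low, or that the arms will be affected differently. The change is worth making because it is cheap and uses contacts and data access already planned.

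**What to change.** - In section 8.2.1, have staff ask the secondary contact about, and record, any SAE including hospitalisation, not only death. This brings the sentence into line with sections 8.2 and 8.6.
- In the same section, name the medical records and hospital data of section 7.3 as an SAE source for the period from randomisation to 3 months, for participants without a completed 3-month questionnaire. Extend the record check in section 7.5.3 to match.
- Report by arm how many participants had 3-month SAE ascertainment and by which route (questionnaire, secondary contact or records), so that readers can judge completeness.

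The cost is a sentence or two in section 8.2.1, a matching phrase in section 7.5.3 and one line in the safety tables, plus the work of checking records for SAEs. The downside is that some events from linked data will arrive late. They would serve the final comparison, not expedited reporting.
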